### **Research Design**

This pilot study will utilize two separate experimental designs to address: 1) the Reach, Effectiveness, Implementation and Maintenance and 2) the optimal delivery method for an in-home exercise intervention program for individuals with PD living in underserved communities. Both studies will utilize paired, randomly assigned groups to explore the given questions. Pairs will be based on disease severity (UPDRS III scores) and age.

Study 1: The proposed pilot study will utilize the RE-AIM framework (Reach, Effectiveness, Adoption, Implementation and Maintenance) to focus on the reach and effectiveness of a 6-month triweekly in-home cycling program and then pilot a health coach model to promote maintenance for the subsequent 3-month period. 40 qualified individuals will be paired based on disease severity (score on subsection III of the UPDRS) and age and randomly assigned to either the cycling group or the normal care control group for 6 months. For those in the cycling group, participants will interact via Skype with study team members during all cycling sessions. This intervention will allow the individuals enrolled to participate in regular exercise and a community activity that promotes social support and engagement. The proposed pilot maintenance model for the 3-month period following the intervention will implement a health coach model with scheduled sessions every other week to discuss goals and motivation while decreasing the total contact time with the participant. Individuals in the normal care control group will crossover and complete the cycling intervention following the initial 6 months.

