### **Baseline**

The baseline assessment is the same for both substudies.

All participants will complete approximately three hours of testing at each testing time point. All testing will occur in the on medication state. Testing will consist of biomechanical, non-motor features and disease severity data from each individual. The following are the specific assessment components for each time point:

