**Baseline assessment (or Pre-test for those assigned to the normal care control group)**

- A. Intake and review of forms
  - a. Review Screening measures (completed prior to arrival)
  - b. Consent form
  - c. Demographic data
  - d. Review medical history (completed prior to arrival)
- B. General Questionnaires
  - a. Review current medication list (completed prior to arrival)
  - b. Physical Activity Scale for the Elderly (Washburn et al., 1993)
  - c. Fall history questions
  - d. Activity Specific Balance Confidence Index (Powell & Myers 1995).
  - e. The MacArthur Scale of Subjective Social Status (Adler, Epel, Castellazzo, & Ickovics, 2000)
- C. Clinical measures
  - a. Review Patient Questionnaire section of the UPDRS (completed prior to arrival)
  - b. Movement Disorder Society Unified Parkinson Disease Rating Scale (MDS-UPDRS) (Goetz et al., 2008)
  - c. New Freezing of Gait Questionnaire (Nieuwboer et al., 2009)
  - d. PASS iADL assessment (Chisholm, Toto, Raina, Holm, & Rogers, 2014)
  - e. Canadian Occupational Performance Measure (Law et al, 1998)
- D. Measures of motor function
  - a. Timed Up and Go test (Posiadlo & Richardson, 1991)
  - b. Four square step test (Dite & Temple, 2002)
  - c. Mini-Balance Evaluation Systems Test (mini-BESTest) (Franchignoni, F., et al, 2010)
  - d. Standardized gait analysis – computerized mat (Pilgram, Earhart, & [name], 2016)
  - e. Gait Analysis – free locomotion.
- E. Measures of non-motor function
  - a. Review the Pittsburgh Sleep Quality Index (completed prior to arrival) (Buysse, 1989)
  - b. Beck Depression Inventory-II (Beck et al, 1996)
  - c. UCLA Loneliness Scale V3 (Russell 1996)
  - d. Perceived Isolation Scale (Chisholm et at, 2014)

All selected assessment tools are valid and reliable and have been previously used to assess individuals over the age of 65 years and/or individuals with PD.

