## Study 1 Intervention

Qualifying participants will be stratified by age and motor symptom severity as assessed by the UPDRS (UPDRS Motor score (+/- 4 points) and then randomly assigned to either the in-home cycling group or the waitlist control group.

For individuals assigned to the control group, pre-testing will occur six-months before the baseline measures are collected (figure 1). This period will allow us to collect normal care control data from each participant prior to their six months in the active phase of the study. During this period, each individual will be contacted weekly by the study team to complete a falls questionnaire. Baseline testing will occur within two weeks of the start of the Intervention. Post-test data will be collected following the 6-month intervention and will occur within 1 week of the last calendar day of the intervention.

Participants will be asked to not begin any new exercise programs once enrolled in the study, but will not be asked to discontinue any current physical activity. Information about current physical activity level will be collected at all time points.

Activity monitors (Garmin VivoSmart 3) will be donned by all study participants throughout the duration of the study starting at the time of either pre-test or baseline assessment depending on group assignment and continuing through the 3-month follow-up. These devices allow for activity monitoring as well as online monitoring of heart rate. Participants will be asked to wear the activity monitors at all times once enrolled in the study. Number of steps taken daily and amount of aerobic activity will be used to compare changes in activity level.

**Cycling** -The initial cycling session will occur in the participant's home within 2-weeks of the baseline assessment. Two members of the testing team will be present. The team will set-up the bike and properly fit it to the individual rider. Additionally, the team will ensure the stationary bike is set-up in a safe and secure manner and in an area free of clutter and dangerous obstacles. Study team member will also set-up and establish a secure connection using the MiFi device at this time. Both groups will be provided with a MiFi wireless internet connection if needed to allow for data collection of cycling and activity monitor data.

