8	22 mins	50 – 70% of max heart rate
9	25 mins	50 – 70% of max heart rate
10	25 mins	60 – 70% of max heart rate
11	30 mins	50 – 70% of max heart rate
12	30 mins	60 – 70% of max heart rate
13	30 mins	60 – 70% of max heart rate
14	30 mins	60 – 70% of max heart rate
15	30 mins	60 – 70% of max heart rate
16	30 mins	60 – 70% of max heart rate
17	30 mins	60 – 70% of max heart rate
18	30 mins	60 – 70% of max heart rate

19	30 mins	60 – 70% of max heart rate
20	30 mins	60 – 70% of max heart rate
21	30 mins	60 – 70% of max heart rate
22	30 mins	60 – 70% of max heart rate
23	30 mins	60 – 70% of max heart rate
24	30 mins	60 – 70% of max heart rate

During the first testing session of each week a study team member will complete a falls assessment with each individual.

Normal Care Control - Individual assigned to the control group will be advised to continue their daily routines during the first 6-months. Following this period, they will complete a baseline assessment and crossover into the cycling group. This period will allow us to collect normal care control data from a randomly assigned, age and disease severity (+/-4 points) matched individual. During this period, each individual will be contacted weekly by the study team to complete a falls questionnaire.

Health Coach: Following completion of the 6-month in-home cycling program, participants will be asked to continue their training program following the same training regime. Half of the individuals in the study will have been randomly assigned within their strata to a health coach mediated maintenance program while the remaining individuals in the strata will be assigned to the self-motivated program. Individuals in the health coach group will be introduced to their assigned health coach during the final week of the 6-month intervention and a schedule of meeting times will be determined. Individuals will meet with their health coach once every other week for 15-minutes during their cycling sessions. Individuals in both groups will be taught how to access the built-in programming options on the bike which allow for use of customized training programs. We will set-up the training program for each individual and make sure that they are fully able access the module. During this period, each individual will continue to be contacted weekly by the study team to complete a falls questionnaire.

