### **Posttest assessment**

All measures listed in the Pre-test assessment protocol will be included at posttest except those measures listed under “Intake and review of forms” and “Screening measures”

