For both studies, we will employ a  $2 \times 2$  repeated measures ANOVA with time and intervention as the factors, to determine the outcomes of the cycling intervention effectiveness aims. Additionally, we will use a time (posttest to 3-month follow-up) by group to examine the effectiveness of the health coach maintenance model. Variables of interest include: total number of completed sessions and session duration; PASS scores, walking velocity, stride length, base of support; gait variables (velocity, stride length, base of support and % of time in double support) and MiniBESTest scores as well as number of falls; and mean daily step count.

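### Study 1: adjusting the end-of-period value for the entry value would usually give a narrower confidence interval than the planned 2x2 ANOVA, at no data cost

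*Combined protocol and SAP*

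**What the plan says.** The section Power and Statistical Analysis gives one model for the effectiveness aims of both studies: a 2x2 "repeated measures ANOVA with time and intervention as the factors". Its list of variables includes PASS scores, gait variables and MiniBESTest. The section does not name the term that carries the treatment effect, and it does not say which two visits form the time factor. No adjustment for the entry value appears anywhere in the document.

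The data needed for such an adjustment are collected:

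- The Baseline section introduces its test battery with "The following are the specific assessment components for each time point". The battery is headed "Baseline assessment (or Pre-test for those assigned to the normal care control group" and includes PASS, the gait analysis and the mini-BESTest.
- The Posttest assessment section states that "All measures listed in the Pre-test assessment protocol will be included at posttest", apart from intake and screening items.
- For the waitlist arm, Study 1 Intervention says that "pre-testing will occur six-months before the baseline measures are collected". The visit labelled baseline in that arm is therefore its end-of-control assessment, just before crossover.

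Power and Statistical Analysis also says that the pilot is not powered. It gives 40 participants (20 per group) for Study 1, expects 15-20% attrition, and intends to use the data to estimate an effect size for the next proposal.

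**The concern.** With two arms and two visits, the interaction in a repeated measures ANOVA compares mean change between arms. A change score subtracts the whole entry value, whatever its correlation with the later value. Unless that correlation is very high, this is too much: noise in the entry value is carried into the result. Regression on the entry value lets the data set the coefficient.

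What is at stake is precision. The main quantitative product of Study 1 is an estimate of the arm difference that will inform a later trial, and an interval from 16 to 20 people per arm is wide to begin with. An analysis that narrows it without another participant or measurement is worth having.

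**Working it through.** **The plan's own figure.** The benchmark of about 27 per group for 89% power comes from earlier work and does not set Study 1's size. It reproduces as a three-group one-way ANOVA with f = 0.4 (89.5% power) or as a one-sided two-arm test at d = 0.8 (89.5%). A two-sided two-arm t-test at 1 SD would give 95.0%. None of this bears on the present point, which takes only the SD from that paragraph.

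**Inputs**

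- n = 20 per arm (Power and Statistical Analysis). With 20% attrition, 20 × 0.80 = 16 per arm.
- SD of forward gait velocity = 0.1 m/s (same section).
- ρ, the correlation between entry and 6-month values: not in the documents. Assumed 0.3, 0.5, 0.7, 0.8 and 0.9.
- Equal variance at both visits and a two-sided 95% interval: assumed.

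**Step 1: what the planned test is.** On a simulated data set of 20 per arm, the interaction F was 0.1963, and the squared two-sample t on change was also 0.1963. The equivalence holds for the interaction term. That this is the term the plan intends is an inference.

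**Step 2: validity.** In 20,000 simulated trials per setting (20 and 16 per arm; ρ 0.5, 0.7, 0.9 and 0.95), type I error was 4.7-5.4% for the change score and 4.7-5.2% for the regression. Both are valid under randomisation.

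**Step 3: variance per person, in units of SD².**

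- Change score: 2(1 − ρ), on 2n − 2 df.
- Regression on the entry value: (1 − ρ²) × [1 + 1/(2n − 4)], on 2n − 3 df. The bracket is the price of estimating the slope: 1 + 1/36 = 1.028 at n = 20, and 1 + 1/28 = 1.036 at n = 16.

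Apart from the bracket, the difference is 2(1 − ρ) − (1 − ρ²) = (1 − ρ)². Chance imbalance at entry is part of this same loss and should not be counted again.

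**Step 4: expected half-width.** Half-width = SD × √(variance factor) × √(2/n) × t × E[s], where E[s] is the small-sample expectation of the estimated SD relative to the true SD. At n = 20, t(38) = 2.024 and E[s] = 0.993 for the change score. For the regression, t(37) = 2.026 and E[s] = 0.993.

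Worked at ρ = 0.5, n = 20:

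- Change: 0.1 × √1.00 × √0.1 × 2.024 × 0.993 = 0.064 m/s.
- Regression: 0.1 × √(0.75 × 1.028) × √0.1 × 2.026 × 0.993 = 0.056 m/s.

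| ρ | Gait half-width, change score (m/s, n = 20) | Gait half-width, regression (m/s, n = 20) | Width ratio, n = 20 | Width ratio, n = 16 |
|---|---|---|---|---|
| 0.3 | 0.075 | 0.062 | 0.818 | 0.821 |
| 0.5 | 0.064 | 0.056 | 0.879 | 0.882 |
| 0.7 | 0.049 | 0.046 | 0.935 | 0.939 |
| 0.8 | 0.040 | 0.039 | 0.962 | 0.967 |
| 0.9 | 0.028 | 0.028 | 0.989 | 0.993 |

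The ratio reaches 1 at ρ of about 0.94 (n = 20) or 0.93 (n = 16).

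**Step 5: how often it helps in a single trial.** The regression interval was the narrower one in 96%, 85% and 52% of simulated trials at ρ = 0.5, 0.7 and 0.9 with 20 per arm, and in 93%, 78% and 46% with 16 per arm.

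**The case against.** The strongest reply is that this is a choice between two valid analyses in a pilot that claims no power. The correlation is unknown. At 0.7 the gait half-width moves by 0.003 m/s and at 0.8 by about 0.001 m/s, and neither is likely to alter a later sample-size decision. That stands, and it is why the point is offered as a free improvement. It does not remove the case for the change: the gain is larger at lower correlations, the cost is negligible, and at ρ = 0.9 nothing material is lost.

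Three stronger readings are tempting, and the documents do not support them.

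- *The planned ANOVA is wrong or biased.* It is not. Under randomisation the interaction test holds its level (Step 2).
- *The ANOVA will compare the wrong visits.* Because the waitlist arm's baseline falls after its control period, a literal baseline-to-posttest comparison would have both arms cycling. The document does not say that this is intended, and Study 1 Intervention describes the control period as supplying comparison data from a "randomly assigned, age and disease severity (+/-4 points) matched individual". The visits are unspecified, not misassigned.
- *The pairing must also be modelled, and would add precision.* Research Design says "Both studies will utilize paired, randomly assigned groups to explore the given questions", while Study 1 Intervention says "Qualifying participants will be stratified by age and motor symptom severity as assessed by the UPDRS", and the analysis mentions neither. No gain from a pair term can be shown from the documents. In simulation, with pairs that predict nothing beyond the entry value, 20% loss and degrees of freedom of intact pairs minus 2, a pair random effect widened the interval by about 2.5% relative to the entry value alone. The correlation at which the overall gain ends then fell to about 0.83. It is not part of this recommendation.

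**Conclusion.** The point holds as a modest efficiency gain for Study 1, limited to PASS, gait variables and MiniBESTest. If the interaction is the tested term and the randomised 6 months is the period, adjusting for the entry value narrows the expected 95% CI by 18%, 12%, 6%, 4% and 1% at ρ = 0.3, 0.5, 0.7, 0.8 and 0.9 with 20 per arm. With 16 per arm the figures are 18%, 12%, 6%, 3% and 1%. Above a correlation of about 0.94 (0.93 with 16 per arm) there is no gain. The size rests on the assumed correlation and on equal variances at the two visits; the m/s figures also rest on the SD of 0.1.

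It does not extend to Study 2. With 6 per arm the same formulas put the break-even correlation at only about 0.73. Falls and step count are also outside it: falls have only a recalled history at entry, and step count has at most about two weeks of wear before cycling starts.

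**What to change.** Replace the Study 1 model for these outcomes with wording such as the following, settled before any outcome data are seen:

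> For PASS, gait variables and MiniBESTest, the value at the end of the randomised 6-month period will be regressed on arm and the entry value, and the arm difference reported with a 95% CI. Entry and end values are baseline and posttest in the cycling arm, and pre-test and the assessment labelled baseline (before crossover) in the waitlist arm.

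This also names the estimate and the visits, which the section now leaves open. The cost is one degree of freedom and a change of analysis text. There is no extra visit, measurement or participant. No change is proposed for Study 2, falls or step count.

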## Specific Aims

### **Study 1**

**SPECIFIC AIM 1:** Examine the reach and maintenance of an in-home cycling program for underserved individuals with PD. Reach will be assessed by examining the demographic characteristics of the individuals enrolled and through the administration of a questionnaire on objective and subjective socioeconomic status to better understand their level of accessibility to services, perceived barriers and economic status. We will also explore the implementation of a health coach to promote effective maintenance of the program after the 6-month intervention. Finally, we will conduct two interviews to better understand strengths and weakness of the program and to better address the needs of the participants in future studies.

**Hypothesis 1a:** Demographic characteristics including race and socioeconomic status of the enrolled participants will not statistically differ from the characteristics of the state of WI.

**Hypothesis 1b:** Feedback from participant interviews will inform future delivery of the in-home cycling program.

**SPECIFIC AIM 2:** Determine the effectiveness of a 6-month in-home, progressive, tele-exercise cycling program and 3-month health coach follow-up for underserved populations of individuals with PD.

**Hypothesis 2a:** Participants will improve performance of activities of daily living from baseline to posttest. These effects will be maintained at 3-month follow-up.

**Hypothesis 2b:** Participants will significantly improve measures of gait and balance performance and non-significantly improve fall rate from baseline to posttest. These effects will be maintained at 3-month follow-up in the group piloting implementation of a health coach, but not in solo follow-up group. Falls data will allow for effect size calculations for future applications.

**Hypothesis 2c:** Activity level as measured by an activity monitor will increase from baseline to posttest. This effect will be maintained at 3-month follow-up in health coach group, but not in the solo group.

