**General Questionnaires:**

Demographic, medical history, PD history and current medication data will be collected from each individual. The demographic form will be sent to the individual's home with the welcome letter and the participant will be asked to complete the form and bring it with them to their visit. This information is necessary for the study as it allows for proper categorization of levadopa equivalent dosage levels which may impact symptom presentation and medical history information which may help to inform if the individual is healthy enough for exercise.

The Physical Activity Scale for the Elderly allows for quantification of current exercise and sedentary behaviors.

As falls are one of the primary variable of interest for the larger study, the Fall history questionnaire will provide data on falls in the previous 6 months as well as the most common mechanisms for falls. During the study falls will be logged weekly. Additionally, the Activity Specific Balance Confidence Index will provide data about how fearful individuals are about falling and how this level of confidence changes with various tasks that are common to everyday living.

The effect of socioeconomic status on exercise practices for individuals with PD in rural and metropolitan underserved communities is one of the primary aims of this study. The MacArthur Scale of Subjective Social Status will be used to assess how perceived status and income related to exercise practices.

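### Falls enter the Study 1 maintenance ANOVA as a count with no denominator; if weekly totals are used, an unchanged fall rate looks like a drop of about half

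*Combined protocol and SAP*

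**What the plan says.** The Power and Statistical Analysis section applies a 2 × 2 repeated measures ANOVA to a list of variables that includes "MiniBESTest scores as well as number of falls". For maintenance in Study 1 it adds a "time (posttest to 3-month follow-up) by group to examine the effectiveness of the health coach maintenance model". It states no source, counting window or denominator for falls. Activity, in the same list, is already expressed as a daily mean of steps.

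The hypothesis is worded as a rate. Study 1, Hypothesis 2b expects participants to "non-significantly improve fall rate from baseline to posttest" and continues: "These effects will be maintained at 3-month follow-up in the group piloting implementation of a health coach, but not in solo follow-up group". It also gives the purpose of the falls data: "Falls data will allow for effect size calculations for future applications".

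Two falls sources are described elsewhere.

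- **Weekly contacts.** The General Questionnaires section says "During the study falls will be logged weekly". The Study 1 Intervention section has weekly falls contact during the control period, the cycling period and the 3-month maintenance period, and in both maintenance groups.
- **Recall.** The baseline list includes "Fall history questions", and the General Questionnaires section says the "Fall history questionnaire will provide data on falls in the previous 6 months". The Posttest and 3-month follow-up sections repeat all baseline measures except intake and screening items, so these questions recur at both visits. No recall window is given for those later visits.

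In Study 2, Hypothesis 2b has weekly calls to both groups. The Study 2 Intervention section describes an assessment at the first session of each week, and then an end-of-week call for the solo group.

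**The concern.** The cycling phase lasts 6 months and the maintenance phase 3 months. A count that is not divided by time observed is therefore not comparable between posttest and follow-up.

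The hypothesis predicts benefit kept with a health coach and lost without one. On undivided weekly totals, a coached group at a steady rate would look as if it had improved further. A solo group whose rate had doubled back would look as if it had held its gain. Someone reading the group means would misjudge both groups, and the effect size carried into later grant applications would be too small. The General Questionnaires section calls falls a primary variable of interest for the larger study, so that effect size is likely to be used.

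**Working it through.** The documents give no fall rate, variance or power for falls, so there is no planned figure to reproduce.

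**Inputs from the documents.** The intervention lasts 6 months, shown as 24 weeks in the progression table (about 26 calendar weeks). Maintenance lasts 3 months (12 to 13 weeks). Study 1 has 40 people, and controls cross over to cycling. Half of all participants are assigned to the coach, so there are 20 per maintenance group before the expected 15–20% attrition.

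**1. Weekly totals at an unchanged rate.** Ratio of expected counts = follow-up weeks ÷ intervention weeks.

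- 12/24 = 0.50
- 13/26 = 0.50
- 13/24 = 0.54
- 12/26 = 0.46

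The apparent drop is 46 to 54% in each group.

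**2. The hypothesised pattern.** Assume the solo rate doubles and the coached rate is steady (the size is an assumption). The solo ratio is 2 × 0.46 to 2 × 0.54 = 0.92 to 1.08, which looks maintained. The coached ratio is 0.46 to 0.54, which looks like further improvement.

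**3. Recall at both visits.** Assume the window is still 6 months at follow-up. Its first half then lies inside the intervention. If the rate changes by a factor r after the intervention, the ratio shown is 0.5 + 0.5r. A doubling shows as 1.5 and a halving as 0.75, so half of any change is lost. There is no false drop.

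**4. False time effect in the ANOVA.** Simulation of the 2 × 2 ANOVA on weekly totals, same unchanged rate in both groups, two-sided 5%, 20,000 runs. Rates are assumed; counts are Poisson, with or without gamma frailty.

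| Falls per person-month | 20 per group | 16 per group |
|---|---|---|
| 0.1 | 47–50% | 38–42% |
| 0.25 | 84–87% | 74–79% |
| 0.5 | 98–99% | 95–98% |

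With equal windows the same test rejects in 5.0%. The group-by-time test stays at about 5% throughout. If the groups have different but constant rates (0.25 against 0.5 per month), it rejects falsely in 16–24%.

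**5. Coach steady, solo rate doubled.** 20 per group, gamma frailty shape 0.5 to 2, 24 weeks against 12 or 13, t tests on change.

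| Mean falls per 24 weeks (assumed) | Solo rise detected: counts | Solo rise detected: rates | Group-by-time power: counts | Group-by-time power: rates |
|---|---|---|---|---|
| 1 | 2–7% | 34–46% | 19–23% | 27–33% |
| 2 | 2–7% | 58–77% | 30–41% | 44–58% |
| 4 | 2–7% | 82–96% | 49–67% | 66–84% |

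The 2–7% is the range across all three means. The group-by-time difference in falls is 0.50 to 0.54 of its equal-window size (for example, about 2.0 to 2.2 falls instead of 4 at the highest mean). The standardised difference on counts is 0.77 to 0.92 of that on rates.

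**6. Baseline to posttest.** Recall against recall compares one 6-month window with another, so nothing is built in. Baseline recall against the weekly log would compare two methods of collection.

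**The case against.** The strongest reply is that this is shorthand. Both Hypotheses 2b name a fall rate, Study 2 ties it to weekly calls, and the analysis section is a brief list of variables. If falls per week was meant, the window problem disappears. That stands, and it limits the point to something one sentence could largely settle. But the section does not say so, and the same list does put steps on a per-day basis.

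A reader might infer more than the documents support, in three ways.

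- **That the plan has no falls source.** It has two; the gap is that the analysis section does not choose between them.
- **That the coach-versus-solo test is invalid.** The planned test is group by time, and it keeps its 5% level when the groups share a rate. Maintenance assignment is randomised within strata, so systematic differences in rate are not expected, although chance imbalance is possible at this size. The false findings lie in the time effect and in within-group readings.
- **That the effectiveness comparison is compromised.** Cycling and control phases are both 6 months.

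It is also fair that the standardised effect shrinks only modestly. At a mean of 1 fall it goes from 0.45–0.49 to 0.36–0.39, a loss of about 0.1, against a standard error of roughly √(2/20) = 0.32. Doubling is the value at which a 2:1 window cancels exactly, so it is the most striking illustration. And weekly records allow a rate to be calculated later, so no data are lost.

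**Conclusion.** The point holds in a bounded form. The analysis section specifies a count where the hypothesis needs a rate. Taken literally with weekly totals, it makes a steady fall rate look like a 46–54% drop from posttest to follow-up, gives a wrong time effect and a wrong within-group reading of maintenance, and about halves the group-by-time difference in falls. Recall at follow-up, if the window is still 6 months, avoids the false drop but hides half of any change.

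The window ratios rest only on the stated phase lengths. The rejection rates, power and standardised effects rest on assumed fall rates, frailty and a doubled solo rate. The documents do not support reading this as an inflated coach-versus-solo test or as a flaw in the cycling-versus-control comparison.

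Severity is minor to moderate. The pilot is expressly unpowered, and falls are expected to change non-significantly. They are, however, collected to supply effect sizes for later work, which is what the raw count would distort.

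**What to change.** - In Power and Statistical Analysis, replace the falls count with falls per week observed, and name the weekly contacts as its source.
- For posttest to follow-up in Study 1, report rate ratios with intervals from a count model with log(weeks observed) as offset and standard errors clustered by person. The offset also handles people who leave early.
- Keep any baseline-to-posttest comparison recall to recall.
- In Study 2, with 12 people, report descriptive rates by group only. Reconcile the three descriptions of how falls are collected: Hypothesis 2b, the first-session assessment, and the end-of-week call for the solo group.

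**Cost.** Protocol wording and a little more analysis work, with no new visits or instruments. The count model is mildly liberal at 20 per group (group-by-time rejection of 4.9–7.2% in simulation when nothing differs). Its intervals will be wide, about ×/÷ 1.6 to 3.1 around the ratio of rate ratios, so the interval should be reported and not the p-value alone. If the sponsor prefers to keep the ANOVA, stating falls per week observed is enough to remove the window problem.
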